7.1.5. Visit 5: 24 hrs after CEA or other intervention (\pm 24 hrs)

- Physical examination/ vital signs
- Review of concomitant medication
- Assessment of AEs including wound healing complications
- Assessment of clinical outcome
- ECG examination
- Assessment of interventional outcome and NIHSS
- Cerebral DWI-NMR post intervention (12-72 hrs after intervention)
- clinical biochemistry, clinical haematology (incl. assessment of bleeding according to RE-LY study group criteria), coagulation and urinalysis

7.1.6. Visit 6: follow up 3 months after treatment (\pm 1 month)

- Physical examination/ vital signs
- Review of concomitant medication
- Assessment of AEs including wound healing complications
- Assessment of neurological status (MRS, Barthel Index, NIH Stroke Scale)
- Assessment of clinical outcome
- ECG examination
- clinical biochemistry, clinical haematology (incl. assessment of bleeding according to RE-LY study group criteria), coagulation and urinalysis
- in vitro bleeding time PFA100 /PFA200 and platelet aggregation assay (response to collagen, ADP and TRAP)
- Pharmacokinetic blood sampling (for approximately 20 % of patients)
 - **T3m** 3 months (\pm 1 month) after IMP infusion
- detection of anti-Revacept antibodies

7.1.7. Visit 7: 12 months telephone follow up (\pm 1 month)

- Assessment of clinical outcome

7.2. Details of Study Procedures

7.2.1. Review of anamnesis

General medical and surgical history (including pre-/ concomitant medication for the last 3 months) will be recorded at screening.

General risk factors (adapted from SPACE-2):

- 1) Blood pressure both arms, if difference > 20/10 mm Hg: angiologic assessment performed (n/y)
 - Heart rate
- 2) Height, weight, BMI
- 3) Physical exercises > 30 min / week (none, 1-2x, ≥ 3x, not known)
- 4) Lab values glucose (fasting), HbA1c, Cholesterine, HDL, LDL, Triglyceride
- 5) Smoking habits
 - Non-smoker
 - Ex-smoker / smoker
 - From (year) to (year)
 - No. cigarettes per day
- 6) Alcohol consumption (y/n), if yes ml/day consumed beer, wine, spirits

7.2.2. Physical examination

Body height will be measured at visit 1. Body weight, heart rate, blood pressure will be recorded at each study visit. The heart rate will taken by feeling the pulse, unless an electrocardiogram is scheduled for the corresponding visit. Blood pressure will be measured once on both arms auscultatorily while the subject is seated, first after 5 minutes of physical and emotional rest. Furthermore, physical examination of heart, lung and abdomen will be performed and any signs of peripheral oedema or ascites will be assessed.

7.2.3. Carotid Endarterectomy

Assessment of CEA (Visit 4)

Detailed CEA specifications will be recorded according to the SPACE-2 study:

- Site of intervention (left/right)
- Anaesthesia (general / local)
- Technique used
- Duration of surgery (minutes)
- Duration of clamping (minutes)
- Degree of residual stenosis
- leakiness at the end of surgery (y/n)

Immediate outcome of CEA will be recorded by assessing:

- Completion of vascularisation procedure
- Discontinuation of vascularisation procedure
 - Prior to carotis opening
 - after probe clamping

Assessment of CEA or intervention outcome (Visit 5)

Adapted from SPACE-2

Complications

- no
- yes
 - Haematoma
 - Other, specify

Further details are given in the CRF formats.

7.2.4. Neurological assessments

See Appendix A for neurological assessment scores. NIH score should be assessed by a certified physician.

7.2.5. Assessment of adverse events

Adverse events will be closely monitored including any unexpected effects on cerebral or myocardial ischemia and bleeding events. Wound healing complications will be documented as part of general adverse event reporting (see also section 8).

7.2.6. Clinical Outcome

Clinical outcome will be summarised cumulatively i.e. before treatment, one and three days after treatment at 3 months and at 12 months. See Appendix B for definitions of clinical events. The following endpoints will be recorded:

- Rate of all cause death
- Rate of stroke-related death
- Any TIA, amaurosis fugax or stroke including haemorrhagic stroke,
- Assessment of cardiovascular outcome including myocardial infarction and re-intervention up to 3 and 12 months

7.2.7. Transcranial Doppler

Central Analysis & Test Run

Each study centre shall send a test dataset to the central core laboratory prior to starting patient recruitment. The core lab will notify the study centre and sponsor of successful completion of a test run. TCD recordings are to be sent to the following core lab for central analysis:

PD Dr. med. [name]
Facharzt für Neurologie
[name]
[name]
[contact]
[contact]

Central analysis will be performed for both TCD datasets recorded for each patient enrolled (i.e. visit 1 and 3).

There is no need for local analysis of TCD recordings. Both TCD recordings are analysed centrally only.

MES detection by TCD

TCD recordings will be made from the middle cerebral artery (MCA), via the trans-temporal route. Each TCD assessment is recorded for one hour as specified below.

All TCD recordings must be performed under similar conditions, i.e.:

- Same apparatus
- Same position of patient
- System settings

All recordings shall be performed with a DWL TCD machine with single-depth 2-MHz transducers. Standard settings should be used. Machine settings shall be adapted to harmonised consensus guidelines (Ringelstein et al., 1998) and agreed upon by all study centers. For TCD recording, patients are to be placed in a sitting or supine position. The MCS will be identified via transtemporal window and a transducer will be attached using a

standard headset. TCD signals are recorded for one hour. The total number of MES per hour will be analysed.

Spectral display and audio signals will be monitored acoustically and visually online by an experienced observer during all recordings. Audio and visual signals will be recorded onto suitable storage media for central analysis.

MES will be identified visually as predominantly unidirectional short-duration intensity increase accompanied by characteristic acoustic clicking, chirping or moaning sounds. A previously agreed threshold will be set at all participating study centres following validation by analysis of standard reference tapes. MES intensity will be measured in dB and be calculated as the ratio of peak intensity of MES divided by the intensity of the background signal. The same algorithm will be used throughout the study. Central offline analysis of all recordings will be performed using the same machine and same algorithm.

7.2.8. Electrocardiogram (ECG)

A 12-lead ECG will be recorded at rest in supine position: unipolar precordial leads V1-V6 (according to Wilson), bipolar limb leads I, II, III (according to Einthoven), and unipolar limb leads aVR, aVL, aVF (according to Goldberger). The following parameters will be collected:

- Type of rhythm
- PQ interval
- QRS complex
- QT interval
- Assessment of ST-segment deviation

7.2.9. DWI-NMR

The following parameters will be recorded:

- Occurrence of new cerebral lesions from baseline (visit 1) to visit 5
- If possible, number of new cerebral lesions developed between baseline (visit 1) and visit 5

7.2.10. Clinical Chemistry: Biochemistry, Haematology, Coagulation (in-house)

Biochemistry

- ALAT/SGPT, albumin, alkaline phosphatase, ASAT/SGOT, blood urea nitrogen, calcium, chloride, creatine phosphokinase / CK-MB or cardiac troponin (selection not to be changes for an individual patient), γ -GT, creatinine, lactate dehydrogenase, glucose, sodium, potassium, total bilirubin, total protein, total cholesterol, triglycerides, uric acid and C-reactive protein (CRP) will be determined.

Haematology

- Haemoglobin, platelet count, haematocrit (where feasible), white blood cell count (WBC) and red blood cell count (RBC), detailed differential hemogram. In case WBC is $< 3.500/\mu\text{l}$ or $> 11.000/\mu\text{l}$ a differential blood count has to be performed i. e., neutrophils, lymphocytes, eosinophils, basophils and monocytes.

Coagulation

- Activated partial thromboplastin time (aPTT), prothrombin time (PT), International normalisation ratio (INR)

7.2.11. Bleeding

Assessment of bleeding will be performed at all visits for which Haematology laboratory parameters are scheduled, in addition to adverse event documentation.

Major bleeding is defined as a reduction in haemoglobin level of at least 20 g per litre, transfusion of at least 2 units of blood, or symptomatic bleeding in a critical area or organ. **Life-threatening bleeding** is a subcategory of major bleeding that consisted of fatal bleeding, symptomatic intracranial bleeding, bleeding with a decrease in haemoglobin level of at least 50 g per litre, or bleeding requiring transfusion of at least 4 units of blood or inotropic agents or necessary surgery. All other bleeding is considered **minor** (Connolly et al., 2009).

7.2.12. Where feasible: PFA 100 / PFA 200 and platelet aggregation

PFA100 / PFA200 and/or platelet aggregation will be performed at all sites capable of performing the said analyses, or within close enough proximity to the advanceCOR laboratory.

Platelet aggregation

In vitro platelet aggregation will be performed after stimulation with collagen, ADP and thrombin receptor activated peptide (TRAP). Details on sample processing, test performance and shipping requirements or logistics will be provided to the individual centres prior to trial initiation.

7.2.13. Urinalysis (in-house)

10 ml urine are to be collected. The following parameters are to be analysed: Total protein, glucose, blood and pH. In case of any abnormality urinary sediment (where feasible) is also to be determined.

7.2.14. Pregnancy test (in-house)

For women of child-bearing potential (WOCBP) a urine pregnancy test (minimum sensitivity 25 IU/L) will be performed at screening (visit 1). Urine pregnancy tests will be supplied by advanceCOR to the study site.

7.2.15. Pharmacokinetic assessment and detection of anti-drug antibodies (at advanceCOR GmbH)

Pharmacokinetic sampling

For pharmacokinetic assessment, several 2 ml serum blood samples will be collected as specified in section 7.

Blood collection at visit 2 must be performed on the opposite arm of administration of study medication. The time points correspond to the time from starting (not finishing) administration of study medication. Times of administration of study medication and blood sampling must be noted both in the patient's notes and case report form.

Pharmacokinetic measurements are required for approximately 10 patients per treatment group, based on the results obtained in the preceding phase I study. advanceCOR will notify study sites as soon as no further pharmacokinetic samples are required.

Sampling for screening of anti-drug antibodies

For measurement of anti drug antibodies, 2 ml of serum blood will be collected at visit 1 and visit 6.

Preparation and Shipment of Samples

Details on sample processing and shipping requirements and logistics will be provided to the individual centres prior to trial initiation.

Analyses of anti drug antibodies and Revacept pharmacokinetics

Analyses of anti drug antibodies and Revacept pharmacokinetics will be conducted at the advanceCOR GmbH according to validated protocols and SOPs effective at that moment in time.

7.3. Safety Assessments

The safety variables are AE, SAE, data from physical examination, routine laboratory results, ECG, blood pressure, antibody production and heart rate. Signs and symptoms present within 2 weeks of starting therapy (regardless of relationship to current disease) will be obtained at baseline. Study drug toxicities will be assessed continuously. Adverse events will be classified as outlined in section 8 below.

[figure not shown]
8. ADVERSE EVENTS

8.1. Definitions

An **Adverse Event (AE)** is defined as any new untoward medical occurrence or worsening of a pre-existing medical condition in a patient or clinical investigation subject that does not necessarily have a causal relationship with this treatment. An AE can therefore be any unfavourable and unintended sign (including an abnormal laboratory finding, for example), symptom, or disease temporally associated with the participation in the clinical trial, whether or not considered related to the investigational product.

Pre-existing conditions, i.e. a disorder present before participation in the clinical trial should not be reported as an adverse event unless the condition worsens or episodes increase in frequency during administration of study medication.

Classifications of Adverse Events and documentation and reporting requirements are visualised in the following scheme alongside the responsibilities of the Sponsor (advanceCOR) and Investigators (see also section 8.3 p. 37).

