6.1.6. Treatment Administration

Revacept/placebo will be administered once per patient by intravenous injection as described in the handling instructions of the study medication. One patient dose is prepared by combining 3 IMP vials of a single kit box. Please equilibrate all vials of a kit box to room temperature before combining them in a 50 ml syringe pump. An in-line filter rated for syringe pump use must be inserted in the syringe pump infusion line. Infusion of IMP should be for 20 minutes.

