8.7. Other Safety Considerations

Any significant worsening noted during interim or final physical examinations and any other potential safety assessments, whether or not these procedures are required by the protocol, should also be recorded on the appropriate nonserious AE page of the CRF or SAE paper CRF page.

Classification of cause specific mortality will be performed according to the guidelines listed in Appendix B.

In addition to the regular SAE reporting requirements described in section 8.3.1, any death of any patient randomised into the study must be reported by the Principal Investigator to the Regulatory authority, leading ethics committee as well as the local ethics committee of the study site at which the patient was enrolled as soon as possible.

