9.3. Statistical Procedures

Safety

The number and proportion of patients experiencing each type of event will be summarised per treatment group. Only treatment-emergent events will be included in the analysis (i.e. those that began or worsened after screening (visit 1)).

The incidence and event (or event grouping) will be summarised and compared between treatment groups using Pearson's chi-squared tests.

Blind Review/Final Statistical Analysis Plan

A blinded review of the data shall be performed within the framework of the requirements of the ICH Guideline E9. The Blind Review Report will include the final statistical analysis plan (updated statistical analysis plan) and the final definition of data sets. If the blind review suggests changes to the principal features stated in the protocol, these should be documented in a protocol amendment.

The Blind Review Report will be finalised before the blind will be broken. Formal records shall be kept of when the statistical analysis plan was finalised as well as when the blind was subsequently broken.

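### Section 8.1 ties the reporting of worsened pre-existing conditions to the 20-minute infusion, which contradicts the protocol's own AE definition and collection rules and leaves non-serious worsening open to inconsistent recording

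*Protocol*

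**What the plan says.** Protocol section 8.1 contains two statements on pre-existing conditions. The first paragraph defines an adverse event as "any new untoward medical occurrence or worsening of a pre-existing medical condition in a patient or clinical investigation subject", and extends it to any sign, symptom or "disease temporally associated with the participation in the clinical trial, whether or not considered related to the investigational product". The time reference there is trial participation. The second paragraph says that a disorder present before participation should not be reported as an AE "unless the condition worsens or episodes increase in frequency during administration of study medication".

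Section 6.1.6 fixes what administration means here: "Revacept/placebo will be administered once per patient by intravenous injection", and "Infusion of IMP should be for 20 minutes". Section 7.2.15 uses the same term for this timed event when it sets the clock for pharmacokinetic sampling.

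Other sections use wider periods:
- Section 8.3.3 starts collection of non-serious AEs at informed consent.
- Section 8.3 asks for a general AE prompt at each visit after treatment, and the schedule in 7.1 lists AEs at Visits 2 to 6.
- Section 8.7 sends "Any significant worsening noted during interim or final physical examinations", and worsening at other safety assessments, to the AE or SAE page.
- Section 9.3 counts as treatment-emergent "those that began or worsened after screening (visit 1").

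**The concern.** The restrictive wording suits a drug taken over weeks, where the period of administration and the period of observation are much the same. Here they are not. Every patient enters with carotid stenosis and a TIA, amaurosis fugax or stroke in the previous 30 days (5.2.1), so every patient has at least one pre-existing condition to which the sentence could apply.

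The second paragraph is also the more specific instruction. A site deciding whether to enter a worsened pre-existing condition may well follow it over the general definition above it. If some sites do and others do not, AE capture differs by site. The SAP (section 3) reports 16 active centres, and centre is not among the minimisation factors in 6.1.7, so site differences in recording are not balanced across arms by design. At stake are the AE tables and the AE part of the data compiled for the DSMB.

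**Working it through.** The plan gives no figure to reproduce. The check compares the sentence with the other rules; the only arithmetic is the length of the literal window.

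**Literal window.** Inputs: 20 minutes (6.1.6); 30 days after dosing for SAEs (8.3.1); Visit 6 at 3 months ± 1 month (7.1), taken as 60 to 120 days on an assumed 30-day month.
- Against the SAE window: 20 / (30 × 1,440) = 20 / 43,200 = 0.05%.
- Against Visit 6 at 60 days: 20 / 86,400 = 0.023%.
- At 90 days: 20 / 129,600 = 0.015%.
- At 120 days: 20 / 172,800 = 0.012%.

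The literal window therefore cannot be reconciled with the collection periods stated elsewhere. These percentages are shares of time, not of missed events.

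**What other rules already catch.**

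| Worsening of a pre-existing condition outside the infusion | Other rule | Captured? |
|---|---|---|
| Serious, from consent to 30 days after dosing | 8.3.1: all SAEs (later ones if believed related to product or procedure) | Yes |
| Clinically significant laboratory result, or one needing corrective therapy | 8.4, which uses anaemia as its example | Yes |
| Significant worsening at an examination or other safety assessment | 8.7 | Yes |
| TIA, amaurosis fugax or stroke | 7.2.5 names cerebral ischaemia in AE monitoring; 7.2.6 records these events to 12 months | Yes, at least as clinical outcome |
| Non-serious worsening between visits, or not judged significant at an assessment | 8.3 prompt only | Not reliably |
| More frequent non-serious episodes of other pre-existing conditions | 8.3 prompt only | Not reliably |
| Non-serious worsening between consent and infusion | 8.3.3 starts collection at consent, but 8.1 read literally excludes it | Contradictory |

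**Why the last three rows stay open.** The prompt in 8.3 is deliberately open-ended, so whether the answer becomes an AE is still decided under 8.1. The rule in 8.3.3 on worsening applies to an ongoing non-serious AE, that is, one already entered. The definition in 9.3 is an analysis filter and cannot recover an event that was never recorded. SAP section 8.5.4 tabulates AEs as reported and adds no treatment-emergent definition. The full check of AE data in protocol 9.2.1 is described as a check of patients' key data, not as a search for omitted events.

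**The case against.** A reader might infer that section 8.1 as a whole makes worsening reportable only during the infusion, so that later worsening of the index disease need not be reported. The documents do not support that. The operative definition in the first paragraph includes "any new untoward medical occurrence or worsening of a pre-existing medical condition" and ties it to trial participation. Appendix B defines ischaemic and haemorrhagic stroke through a new focal deficit, so a recurrent stroke is a new occurrence and not a pre-existing condition. TIA, amaurosis fugax and stroke are collected as clinical outcomes whatever the AE page says. Section 1.3 gives the DSMB clinical endpoints and laboratory values as well as AEs, so index-disease events and laboratory changes reach it by another route.

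It can also be said that the sentence is leftover template text, much like the mention of a placebo lead-in period in 8.3.3, and that sensible sites would ignore it. That may be true at many sites, but nothing in the documents shows it, and the text is an operative instruction.

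Two further inferences should be resisted. The time shares above do not measure harm. The documents also give no figure for how common worsening of pre-existing conditions is among expected events, or for how many patients have hypertension.

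What stands from this side is that the gap is narrow. What it does not remove is the contradiction between two adjacent paragraphs, or the three open rows in the table.

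**Conclusion.** Wrong as written: an internal inconsistency that should be corrected. The second paragraph of 8.1 conflicts with the first paragraph, with 8.3.3, with 8.7 and with 9.3. The practical exposure is mainly non-serious worsening, or more frequent episodes, of pre-existing conditions after the infusion or between consent and infusion. The number of affected AEs cannot be derived from the documents.

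The conclusion assumes that at least some sites apply the sentence as written. If none did, the defect is editorial only. Because the trial is double-blind, a site's reading should not depend on the arm. The expected effect is therefore lower counts in all arms and added variation between sites; the documents give no reason to expect a bias towards one arm.

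**What to change.** 1. In the second paragraph of 8.1, replace the reference to administration with: *at any time during the AE collection period (from informed consent to Visit 6)*. Visit 6 is the last visit at which the schedule lists AEs. Leave 9.3 unchanged: it already covers worsening after Visit 1, and moving its start to the infusion would be a separate decision about what counts as treatment-emergent.
2. The SAP of 10.06.2019 describes enrolment and visits in the past tense, so new wording alone cannot change what sites recorded. At the blinded data review (SAP 7.2), run a programmed cross-check of the NIHSS, Rankin, vital-sign, bleeding, laboratory and clinical-outcome pages against the AE pages. Set the rules for what counts as worsening before the check is run, and query sites on unmatched cases before database lock.
3. State any under-capture that cannot be resolved as a limitation in the study report. The cross-check will not find worsening that left no trace on another page.

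Cost: one sentence and one program on data already collected. The downside is some extra site queries and a few more AE entries in all arms.

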8.1.1. Serious Adverse Events

A **serious AE (SAE)** is any untoward medical occurrence that at any dose:

- results in death
- is life-threatening (defined as an event in which the subject was at risk of death at the time of the event; it does not refer to an event which hypothetically might have caused death if it were more severe)
- requires inpatient hospitalisation or causes prolongation of existing hospitalisation (see note below for exceptions)
- results in persistent or significant disability/incapacity
- is a congenital anomaly/birth defect
- is an important medical event (defined as a medical event(s) that may not be immediately life-threatening or result in death or hospitalisation but, based upon appropriate medical and scientific judgment, may jeopardise the subject or may require intervention [eg, medical, surgical] to prevent one of the other serious outcomes listed in the definition above.) Examples of such events include, but are not limited to, intensive treatment in an emergency room or at home for allergic

bronchospasm; blood dyscrasias or convulsions that do not result in hospitalisation.)

All pregnancies, regardless of outcome, must be reported to the sponsor on a Pregnancy Report Form, not an SAE form.

The following hospitalisations are not considered SAEs in advanceCOR GmbH clinical studies:

- a visit to the emergency room or other hospital department < 24 hours, that does not result in admission (unless considered "important medical event" or event life threatening)
- elective surgery, planned prior to signing consent
- admissions as per protocol for a planned medical/surgical procedure
- routine health assessment requiring admission for baseline/trending of health status (e.g. routine colonoscopy)
- medical/surgical admission for purpose other than remedying ill health state and was planned prior to entry into the study. Appropriate documentation is required in these cases
- admission encountered for another life circumstance that carries no bearing on health status and requires no medical/surgical intervention (e.g. lack of housing, economic inadequacy, care-giver respite, family circumstances, administrative)

